## 2.0 Objectives\*

The primary objective is to test the effect of an individualized exercise oncology program on healthcare utilization, 30-day hospital readmission, pain, and cancer treatment tolerance.

H1: Among women newly diagnosed with stage 0, 1 or 2 breast cancer, those enrolled in an individualized exercise oncology program will have fewer emergency room (ER) visits, fewer hospital encounters, fewer 30-day hospital readmissions, fewer breaks in cancer treatment, less pain, and better cancer treatment tolerance than those in the control group over 3 months.

The secondary objective is to examine the feasibility of an individualized exercise oncology program via adherence and attrition rates.

H2: Among women newly diagnosed with stage 0, 1 or 2 breast cancer and enrolled in an individualized exercise oncology program, adherence to scheduled exercise sessions will average 70% or more, and program attrition will average 70% or less over 3 months.

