## **4.0 Study Endpoints\***

### Primary Study Endpoints:

- Total number of missed fractions, determined via EMR
- A break in cancer treatment, defined as missing  $\geq 3$  fractions due to patient condition, determined via EMR
- ER visits, as determined via EMR
- Inpatient and outpatient hospital encounters, as determined via EMR
- Hospital readmission for the same presenting issue, as determined via EMR
- Hospital length of stay (if hospitalized), as determined via EMR
- Cancer treatment adherence, determined via EMR
- Medications for cancer treatment symptom management, determined via EMR
- Cancer treatment-related side effects, determined via EMR
- Patient-rated pain measured by visual analog scale, as determined via EMR
- Cancer treatment tolerance, measured by the Eastern Cooperative Oncology Group (ECOG) Performance Status score, as determined via EMR
- Quality of Life, as measured by the McGill Quality of Life Measure, administered in-person at weeks 1 and 12  
[\(http://www.npcrc.org/files/news/mcgill\\_quality\\_of\\_life.pdf\)](http://www.npcrc.org/files/news/mcgill_quality_of_life.pdf)

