### Demographic and Baseline Clinical Characteristics:

- Age, as determined via electronic medical record (EMR)
- Diagnosis and diagnostic stage, as determined via EMR
- Diagnosis Date, as determined via EMR
- Body mass index, as determined by height and weight in EMR
- Comorbid chronic conditions (hypertension, diabetes, COPD), as determined via EMR
- Race/ethnicity, as determined via EMR

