## **16.0 Potential Benefits to Subjects\***

Participants in the exercise intervention may experience reduced pain and relief from other effects of cancer treatment, thus reducing breaks in treatment and hospital or ER visits. Participants may also experience improved energy and mood and may establish a positive behavioral pattern of physical activity that will extend beyond the study.

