## **17.0 Data Management\* and Confidentiality**

### Data Management:

All study parameters from the EMR will be downloaded by an EMR specialist via a report, de-identified, and housed in a Microsoft Excel database. Patient forms, including consent forms, will be stored in a locked file cabinet at Maple Tree Cancer Alliance. All patients will be assigned a Study ID number and a list linking patient names to Study ID number will be kept separately from the study data, on a password-protected computer. Data from patient forms will be entered into the master Microsoft Excel spreadsheet. Only Study ID will be used to identify patients in the spreadsheet.

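### Pain, a primary endpoint in H1, is read from routine-care VAS scores with no assessment time, baseline or selection rule, so visit patterns that differ by arm can bias the comparison in either direction

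*Combined protocol and SAP*

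**What the plan says.** Pain is in the primary objective. H1 (section 2.0) predicts "less pain, and better cancer treatment tolerance than those in the control group over 3 months". In section 4.0 its whole definition is "Patient-rated pain measured by visual analog scale, as determined via EMR".

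Other sections narrow down where the scores come from:
- Section 8.0 names only quality of life and exercise adherence as information gathered outside the EMR.
- Section 9.0 has the EMR abstracted after every patient has finished.
- Section 17.0 states the method: "All study parameters from the EMR will be downloaded by an EMR specialist via a report".
- Section 24.0 gives control patients usual care only.

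The baseline list in section 4.0 runs from age to race/ethnicity. It includes items such as "Comorbid chronic conditions (hypertension, diabetes, COPD), as determined via EMR" but no pain score. By contrast, the McGill questionnaire is "administered in-person at weeks 1 and 12".

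Section 17.0 compares continuous endpoints by a t-test or a Mann-Whitney test. It adjusts only for baseline characteristics that differ significantly between groups.

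**The concern.** A routine-care score exists only when a patient is seen, and it reflects why she was seen. The trial expects its intervention to change those occasions: H1 predicts "fewer emergency room (ER) visits, fewer hospital encounters, fewer 30-day hospital readmissions", and section 16.0 expects relief of pain and other treatment effects, "thus reducing breaks in treatment and hospital or ER visits". An ER score taken because a woman is unwell will tend to be high. If one arm has fewer such scores, its recorded pain can be lower even though pain at comparable times is the same.

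Randomization does not protect against this, because the sampling happens after assignment. Adjusting for baseline characteristics does not remove it either. At stake is whether the pain part of H1 can be interpreted. The trial is also open-label, so a choice among scores made after extraction would be made without blinding.

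**Working it through.** **No figure to reproduce.** The only power statement (section 12.0) concerns missed fractions. The documents give no VAS distribution and no visit rates, so every clinical input below is an assumption. Only the 35 per arm and the two-sided alpha of 0.05 come from the protocol.

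**Step 1: size of the spurious difference.** Assume true pain of 2/10 at scheduled visits in both arms and 7/10 at ER visits, *k* scheduled scores per patient, and a Poisson number *e* of ER visits with mean λ. If the endpoint is the patient's mean of all recorded scores, its expectation is

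2 + 5 × E[e/(k + e)].

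For k = 3 and λ = 1.0, the terms for e = 1 to 6 are 0.0920 + 0.0736 + 0.0307 + 0.0088 + 0.0019 + 0.0003 = 0.2073, which adds 5 × 0.2073 = 1.04 points. For λ = 0.5 the sum is 0.1135, which adds 0.57. The spurious difference is 1.04 − 0.57 = 0.47 points.

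**Step 2: false rejection rate.** Add a between-patient SD of 1.5 and a visit SD of 1, with 35 per arm, and simulate with no true difference at scheduled visits. The ranges cover whether an ER score carries the patient's usual pain level and whether scores are truncated to 0-10.

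| Scheduled scores | ER visits per patient, control to exercise | Spurious difference (Step 1) | False rejection (nominal 5%) |
|---|---|---|---|
| 3 | 1.0 to 0.5 | 0.47 | about 20-26% |
| 3 | 0.5 to 0.25 | 0.27 | about 10-12% |
| 8 | 1.0 to 0.5 | 0.24 | about 9-13% |
| 8 | 0.5 to 0.25 | 0.13 | about 5-7% |
| 15 | 0.5 to 0.25 | 0.08 | about 5-7% |
| 3 | 0.2 to 0.1 | 0.12 | about 5-7% |

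Using scheduled-visit scores only, the rate is about 5-6%.

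**Step 3: dependence on the undefined summary.** A second simulation used milder assumptions: mean pain 3, both SDs 1.5, about 6 routine scores, ER scores 3 points higher, Mann-Whitney test. It counted only false findings of less pain with exercise (nominal 2.5%). With ER visits halved from 0.5, 1 or 2 per patient:
- mean score: −0.10, −0.20 or −0.31 points; 4%, 7% or 12%
- worst score: −0.29, −0.49 or −0.67 points; 8%, 17% or 28%

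With no ER visits and routine scores halved from 8 to 4, the worst score still shifts by −0.67 points (30%), and the mean does not shift. With ER visits (1 to 0.5) and routine scores (8 to 4) both halved, the mean shifts by only −0.01 (3.4%).

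**Step 4: direction.** Using the Step 1 formula, suppose control patients have 8 scheduled scores and 1.0 ER visits, and exercise patients have 3 and 0.5. Expected recorded means are 2 + 0.505 = 2.505 and 2 + 0.567 = 2.567. The exercise arm now looks slightly worse despite having half the ER visits.

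**Step 5: after the fix.** One score per patient at a fixed time gave false rejection of 4.5-5.4% in the second simulation. For ANCOVA on the first score, the effect detectable with 80% power is (1.96 + 0.842) × √(2(1 − r²)/35). That is d = 0.67 unadjusted, and 0.64, 0.58 or 0.48 for an assumed baseline correlation of 0.3, 0.5 or 0.7.

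**The case against.** A reader might infer that fewer visits will by themselves make exercise look better on pain. The documents do not support that. They name no summary of the scores. For the mean it is the mix of visit types that matters, not their number: the bias is near zero when all types fall in proportion, and Step 4 shows it can reverse. H1 predicts falls in both ER visits and hospital encounters, so a roughly proportional fall is plausible. Only for a summary such as the worst score does the number of visits suffice.

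The largest rates also need about one ER visit per control patient in 12 weeks and only three routine scores. A woman in daily radiotherapy may have many routine scores, and the effect then almost vanishes.

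That ER scores enter the endpoint is an inference. The text says only that the EMR is the source, although nothing restricts the visit type. Fewer ER visits may also partly reflect a real reduction in pain, but the endpoint cannot separate that from a change in sampling.

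Finally, pain is one of twelve listed primary endpoints and is not the one used for sample size. These points limit the size and certainty of the bias. They do not supply an assessment time, a baseline or a selection rule.

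**Conclusion.** The point stands as an endpoint defined only by its source, in a trial that expects its intervention to change when that source is sampled. The 3-month window in H1 is a period, not an assessment time. Bias in either direction is possible, and the planned tests cannot remove it. Its size cannot be derived from the documents: under the stated assumptions false rejection runs from nearly nominal (about 5-7%) to about 20-26% for the mean score, and a worst-score summary is more exposed. The case for acting rests less on any one of these figures than on the cheap remedy available and the fact that routine scores cannot be standardized afterwards. ECOG status, which measures the treatment-tolerance part of H1, is also taken from the EMR without a time point and has the same gap.

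**What to change.** - **Section 4.0:** replace the EMR source for pain with a patient-completed VAS, given to both groups at the week 1 and week 12 McGill contacts. Require the first score before the first exercise session, since week 1 as written need not precede it. Name the week 12 score as the pain endpoint and add the first score to the baseline list.
- **Section 17.0:** analyse the week 12 score by ANCOVA on the first score, and state how a missing week 12 score is handled.
- **EMR pain scores:** keep as descriptive only, limited to scheduled oncology visits.
- **ECOG status:** specify an assessment time and a rule for choosing among recorded values.

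The cost is about a minute of patient time per contact and a small amendment. Pain between the two contacts is no longer part of the endpoint. The score remains patient-reported in an open-label trial, which this change does not alter.

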## **10.0 Inclusion and Exclusion Criteria\***

Patients will be selected according to the Consolidated Standard of Reporting Trials criteria. Criteria not determined via EMR are determined via the form in Appendix B. Inclusion criteria are:

- Female; determined from electronic medical record
- Initial stage 0, 1 or 2 breast cancer diagnosis within the past 12 weeks determined from electronic medical record
- Age 30-80; determined from electronic medical record
- Physician clearance to participate in exercise

Exclusion criteria are:

- Participation in supervised physical exercise within 6 months prior to study enrollment
- Currently pregnant or planning to become pregnant
- Non-English speaking
- Unable to make own medical decisions and/or to follow verbal instructions

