## 15.0 Risks to Subjects\*

The risks associated with the study intervention are commensurate with light to moderate physical activity, such as muscle soreness. Given the low-impact nature of the exercise and the one-on-one supervision during exercise sessions, the risk of injury or another adverse outcome is very low. Participants in the Exercise Group will have an exercise program individualized to their needs and physical abilities, and participants will be closely monitored during exercise sessions. The

**PROTOCOL TITLE:** Randomized, Controlled Trial of an Individualized Exercise Oncology Program for Newly Diagnosed Breast Cancer Patients

study will not be blinded; patients and treating physicians will be aware of group status and if the treating oncologist recommends the subject stop physical activity, the subject will be withdrawn from the study.

The Exercise Group may incur some travel costs to attend exercise sessions.

No psychological, social, or legal risks are anticipated.

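### The tolerance part of H1 is decided by ECOG performance status, a rating of daily function, although endpoints that bear directly on tolerance are already in the primary list

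*Combined protocol and SAP*

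**What the plan says.** Section 2.0 states the primary objective as the program's effect on "healthcare utilization, 30-day hospital readmission, pain, and cancer treatment tolerance". H1 then predicts, among other things, "fewer breaks in cancer treatment, less pain, and better cancer treatment tolerance than those in the control group over 3 months". Tolerance is thus one of four domains in the objective and one of six predictions in H1, and H1 lists it apart from breaks in treatment.

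Only one endpoint in Section 4.0 carries the tolerance label: "Cancer treatment tolerance, measured by the Eastern Cooperative Oncology Group (ECOG) Performance Status score, as determined via EMR". No rater, assessment time or summary measure is given for it. ECOG is not in the Section 4.0 list of demographic and baseline clinical characteristics.

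The same primary list also has "Total number of missed fractions, determined via EMR", a break endpoint based on three or more missed fractions "due to patient condition, determined via EMR", and "Cancer treatment adherence, determined via EMR". It further includes treatment side effects and medications for symptom management.

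Section 15.0 says that "patients and treating physicians will be aware of group status". The analysis plan in Section 17.0 gives tests for continuous and nominal endpoints and does not say how an ordered score such as ECOG is handled.

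**The concern.** A performance status score describes what a patient can do day to day, in a few ordered grades. (This is general knowledge of the scale; the protocol does not describe it.) It does not record whether treatment was completed, interrupted or stopped, or what side effects it caused. Two women with the same score may have received all or only part of their planned treatment.

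The label determines what the trial may claim. As the plan stands, a difference in ECOG supports a statement that exercise improved treatment tolerance, whatever the delivery and side-effect endpoints show. In the same way, no difference in ECOG would be reported as no effect on tolerance, even if those endpoints favoured exercise.

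The source of the score adds to this. A functional rating taken from routine records in an open-label exercise trial is open to influence from knowing that the patient is exercising, because that activity is close to what the scale rates.

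**Working it through.** No arithmetic decides this point, and the plan states no figure for ECOG. The check sets the predictions in H1 against the twelve primary endpoints in Section 4.0.

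| Primary endpoint (Section 4.0) | What it records | Prediction in H1 |
|---|---|---|
| ER visits; hospital encounters; readmission | Use of care | Named, one prediction each |
| Length of stay | Use of care | None; fits the utilisation domain |
| Pain (visual analog scale) | Symptom | Less pain |
| Break in treatment | Delivery, with a reason attached | Fewer breaks |
| ECOG performance status | Daily function | Better tolerance |
| Missed fractions | Delivery (radiation) | None of its own |
| Treatment adherence | Delivery (not further defined) | None |
| Treatment side effects | Toxicity | None |
| Symptom medications | Toxicity, indirectly | None |
| Quality of life | Quality of life | None |

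1. **Which endpoint decides tolerance?** Only the ECOG item carries the label. H1 gives breaks a separate prediction, so tolerance is not defined through breaks either.
2. **Is direct evidence collected?** Yes. Missed fractions, breaks, adherence, side effects and symptom medications make five endpoints. Four of the five (all but breaks) have no prediction of their own in H1, although the tolerance domain is where they most naturally belong.
3. **Would a difference in delivery be lost?** No. Section 17.0 compares endpoints between groups whatever ECOG shows.
4. **Who rates ECOG?** The documents do not say. The score comes from the medical record, and Section 15.0 says treating physicians know the group. Rating by an unblinded clinician is a fair inference, not a stated fact.
5. **Is there a starting value?** ECOG is absent from the baseline items, and Section 17.0 adjusts only for baseline characteristics that differ significantly. A chance imbalance in starting ECOG would be neither seen nor adjusted for. Randomisation still makes the follow-up comparison valid; a baseline score would add precision and show any imbalance.

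**The case against.** The strongest reply is that this is only a label. Every direct measure of tolerance is already a primary endpoint and will be reported, so a careful reader will see the full picture. That stands as far as loss of information goes. It does not remove the problem, because the label decides which result supports the tolerance statement in H1.

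A second reply is that changing the measure does not remove bias: physicians who know the group also decide on treatment changes and record the reasons. That also stands. The change reduces reliance on a subjective functional rating but does not remove the risk.

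A reader might draw three stronger conclusions that the documents do not support:

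- **That the tolerance question goes unanswered, or that ECOG scores will be read as tolerated or not tolerated.** The five direct endpoints are in the plan, and the protocol sets no cut on ECOG.
- **That ECOG has no room to show an effect.** Section 10.0 requires "Physician clearance to participate in exercise" and early-stage disease, so good entry scores are likely, but ECOG is not an entry criterion. H1 compares the groups over 3 months and does not require improvement from baseline. If function worsens during treatment, less worsening with exercise could still be seen.
- **That power calculations show ECOG to be the wrong measure.** Suppose 20% of controls and 10% of exercise patients score 1 or more. With 35 per group and an uncorrected chi-square test at .05, exact enumeration gives power of 0.219. The proportions are assumed, and any yes/no outcome at those rates has the same power. A bias calculation is no firmer. If rating alone moved the exercise group from 20% to 5%, the test would be significant with probability 0.517, but this needs (20 − 5)/20 = three quarters of those patients to be misrated. A shift from 20% to 15% gives 0.084, not far above .05.

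**Conclusion.** The point holds as a mismatch between a claim and its measure. One of the four domains in the primary objective, and one of the six predictions in H1, is tied to a score that does not record the thing named. Endpoints that do bear on it sit in the same list without that role. The lack of a named rater, assessment time, baseline value and ordinal analysis weakens the ECOG comparison further, even as a measure of function.

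The harm is limited to what may be concluded about tolerance. Differences in treatment delivery or side effects would still be analysed, and no other domain is affected. No numerical size can be given, because the documents contain no ECOG distribution. The conclusion rests on two things outside the text: the general meaning of a performance status score, and the inference that treating clinicians record it. The mismatch itself needs only the first.

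**What to change.** Make these changes before the EMR data are abstracted:

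1. In Section 4.0, rename the ECOG item performance status and stop using it for the tolerance claim. State who records it and which follow-up score is used.
2. In Section 2.0, state that the tolerance part of H1 is judged on the treatment-delivery and side-effect endpoints already listed, among women with treatment due in the 12 weeks. The restriction is needed because Section 10.0 does not require radiation or systemic therapy, and a woman with none due cannot miss any. Say whether breaks, which have their own prediction, also count here, and how the result will be worded if the endpoints disagree.
3. Add the last ECOG before randomisation, from the EMR, to the baseline items. Compare follow-up ECOG between groups adjusting for it with an ordinal method, such as a proportional-odds model, and add this to Section 17.0.

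A new yes/no composite of full delivery is not needed. It would require items that are not listed (dose reductions, delays and their reasons) and would be undefined for women with no treatment due.

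The cost is protocol wording and a small amount of extra EMR abstraction. Some baseline ECOG scores may be missing, and the sponsor gives up reporting an ECOG difference as a tolerance gain.

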## 5.0 Study Intervention/Investigational Agent

### Exercise Group

The study intervention is a supervised, individualized exercise oncology program described in previous literature and provided by Maple Tree Cancer Alliance, a non-profit organization providing exercise training to individuals with cancer (<https://www.mapletreecanceralliance.org/>). This organization was founded in 2011 and currently operates in 9 hospitals serving Ohio and Pennsylvania, offering free exercise programs and nutritional guidance to approximately 500 patients annually to help relieve side effects related to cancer treatment.

Patients in the supervised, individualized exercise oncology program (Exercise Group) will complete a 60-minute exercise session once per week for 12 weeks at Maple Tree Cancer Alliance. The exercise sessions will be individualized to the patient's needs and fitness level by a trainer with a bachelor's degree in exercise science and a national certification for exercise oncology. A patient will work with the same trainer throughout the study, who will plan the patient's individualized exercise regimen, and who will provide one-on-one supervision for the duration of each 60-minute session. Each 60-minute session will include cardiovascular, strength, and flexibility training.

Cardiovascular exercise will be performed on a treadmill. The intensity level for the aerobic exercise ranges from 30-45% of the individual's predicted VO2max, controlled by heart monitors (model S810i; Polar Electro) and lasting 30 min. Strength training will involve a full body workout, with emphasis on all major muscle groups and employing machines, free weights, and resistance tubing. Patients will complete 3 sets of 10 repetitions for each strength exercise. Flexibility training will involve static stretching of all major muscle groups for 15-20 seconds at the completion of each workout.

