## 6.0 Procedures Involved\*

The study design is an open-label, randomized, controlled, parallel-group trial. Women age 30-80 with a recent diagnosis of stage 0, 1 or 2 breast cancer who meet inclusion and exclusion criteria will be invited to participate. As is typical and customary, a diagnosis within the last 12 weeks will be considered a recent diagnosis. Upon study enrollment and informed consent, patients will be randomly assigned to the Exercise Group or the Control Group. Random assignment will be conducted in blocks of 10 to ensure equal groups (See Appendix A). Participants will be enrolled in the study for 12 weeks.

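### The first quality-of-life questionnaire is set for week 1 and nothing places it before open-label assignment, so any analysis that uses that score as a starting value is open to bias

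*Combined protocol and SAP*

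**What the plan says.** - **Measurement times.** Section 4.0 (Primary Study Endpoints) has "Quality of Life, as measured by the McGill Quality of Life Measure, administered in-person at weeks 1 and 12". No week-0 or pre-assignment administration appears anywhere. Section 8.0 confirms that all patients, not only the Exercise Group, provide this measure.
- **Assignment.** Section 6.0: "Upon study enrollment and informed consent, patients will be randomly assigned to the Exercise Group or the Control Group". No assessment is named between consent and assignment.
- **Blinding.** Section 6.0: "The study design is an open-label, randomized, controlled, parallel-group trial". Section 15.0 adds that "patients and treating physicians will be aware of group status", without saying when patients are told.
- **Intervention.** Section 5.0: exercise patients "will complete a 60-minute exercise session once per week for 12 weeks at Maple Tree Cancer Alliance". Section 6.0: "Participants will be enrolled in the study for 12 weeks". The study period and the course of sessions therefore have the same length.
- **Consent route.** Section 22.0 provides an in-person consent meeting in a private room at a cancer center. It also lets patients take the form home and report their decision by phone.
- **Baseline variables.** The Section 4.0 list headed "Demographic and Baseline Clinical Characteristics" contains age, diagnosis and stage, diagnosis date, body mass index, comorbidities and race/ethnicity. Quality of life is not on it.
- **Analysis.** Section 17.0 compares continuous endpoints between groups by t-test or Mann-Whitney test. Statistical control is reserved for baseline characteristics that differ significantly. How the week-1 and week-12 scores are to be combined is not stated.

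**The concern.** Quality of life is self-reported, and patients know which arm they are in. A first score collected after assignment can already differ between arms for three reasons: controls may be disappointed, exercise patients may be hopeful, or a first session may have had some effect. With only two measurements, the obvious use of the first is as a reference for the second. If the reference has moved with the assignment, subtracting it or adjusting for it no longer corrects for chance imbalance alone. It can also remove part of what the trial wants to estimate. A pre-assignment score that was never collected cannot be recovered afterwards.

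**Working it through.** **1. Order of events.** Set side by side, the sections give: consent, then assignment upon consent (6.0), then weekly sessions over 12 weeks (5.0), with questionnaires at weeks 1 and 12 (4.0). If study weeks and session weeks coincide, week 1 is the week of the first session. For a patient who decides at home and phones in (22.0), assignment upon that decision would precede any later in-person questionnaire unless assignment or its disclosure is held back. No such hold is written. Section 23.0 requires a signed form but does not say when a phone consenter signs. The order could therefore differ between patients.

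**2. What a shifted week-1 score does.** Work in SD units with equal SDs at both visits. Let the week-1 group difference be s = t1 + e1 (early treatment effect plus expectation effect). Let the week-12 difference be τ + e12 (true effect plus any expectation effect remaining).

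- Week 12 only: τ + e12. Week-1 timing does not enter.
- Change score: τ + e12 − s. The contribution of week 1 is −s.
- ANCOVA: τ + e12 − ρs, where ρ is the correlation between the two scores. The contribution of week 1 is −ρs.

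If t1 = 0 and the expectation effect persists unchanged (e12 = e1), the change score returns τ exactly, so subtraction then removes a bias. The distortion is harmful when t1 is not zero, or when e1 has faded by week 12.

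**3. Size.** The documents supply neither s nor ρ. Assumed: s = 0.1 to 0.3, ρ = 0.5 to 0.7.

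- Change score: 0.1 to 0.3 SD.
- ANCOVA: 0.5 × 0.1 = 0.05 SD to 0.7 × 0.3 = 0.21 SD.
- Against an assumed true effect of 0.5 SD, ANCOVA loses 0.05/0.5 = 10% to 0.21/0.5 = 42%. The upper figure combines the largest shift with the largest correlation.

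**4. Effect on power (illustration).** The plan's only power figure is 80% for a medium effect on missed fractions (Section 12.0). It does not concern quality of life, and this point does not rest on it. It is also not reproduced at an assumed medium effect of 0.5 SD: 35 per arm, two-sided 0.05, gives 54% by the exact t-test. That is a separate matter. With 35 per arm, 80% power needs 0.68 SD, so 0.68 is taken here as the assumed true week-12 effect. Let a share f of it be present at week 1, with ρ = 0.5. The change score keeps 1 − f of the effect (SD of change √(2(1 − 0.5)) = 1). ANCOVA keeps 1 − 0.5f (residual SD √(1 − 0.5²) = 0.87).

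| f | Change score: effect kept, power | ANCOVA: effect kept, power | Week 12 only: power |
|---|---|---|---|
| 0 | 100%, 80% | 100%, 90% | 80% |
| 0.10 | 90%, 71% | 95%, 87% | 80% |
| 0.25 | 75%, 56% | 87.5%, 81% | 80% |
| 0.50 | 50%, 29% | 75%, 68% | 80% |

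The assumed 0.1 to 0.3 SD corresponds to f of 0.1/0.68 = 0.15 to 0.3/0.68 = 0.44. In this setting a clean pre-assignment score raises power from 80% to 90%. At f = 0.25 that gain is almost gone, and the estimate is 12.5% too small.

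**The case against.** The strongest reply is that several steps here are inferred. The protocol does not define when week 1 begins or when patients learn their group. A questionnaire handed out at the consent meeting, before assignment, would also fit the wording. A reader might infer that the protocol knowingly measures after disclosure. The text leaves the order open, and a post-assignment score is only its most natural reading.

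A reader might also infer that the planned analysis is biased, or that the baseline table is contaminated. Neither follows. Section 17.0 names no change score and no ANCOVA, and a plain week-12 comparison fits its wording and escapes the problem. The week-1 score is never called a baseline. The listed baseline items are record-based characteristics that knowledge of assignment would not be expected to alter.

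Nor can every week-1 shift be called true effect subtracted, since a persisting expectation effect is itself a bias. Any genuine early effect would come from about one session. Finally, quality of life is one of twelve listed primary endpoints. It is in neither the stated primary objective nor H1, and it does not drive the sample size.

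All of this limits the size and certainty of the point. What remains is that nothing secures a pre-assignment score for a self-reported endpoint in an open-label trial, and phone consent makes a uniform order unlikely without a written rule.

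**Conclusion.** The concern holds as a weakness in procedure, not as a demonstrated bias. As written, the only early quality-of-life score may be taken after assignment is known and after the first session, and its order relative to assignment may vary between patients. If it enters a change score or an adjustment, the distortion would be 0.1 to 0.3 SD or about 0.05 to 0.21 SD respectively, under an assumed week-1 difference of 0.1 to 0.3 SD and correlation of 0.5 to 0.7. This applies only so far as the difference is an early treatment effect or has faded by week 12. The direction is towards the null if the early effect has the same sign as the final one. If only week 12 is compared, there is no distortion from this source, but there is then no assured pre-treatment score to adjust for. Because a few sentences in the protocol settle it, this is a cheap improvement.

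**What to change.** State in Sections 4.0 and 6.0 that the first McGill questionnaire is completed in person after consent and before the assignment is disclosed, and call it the baseline score. Keep week 12 as it is. In Section 17.0, specify that the week-12 score is compared between groups adjusted for this pre-assignment score, whether or not the groups differ significantly on it. Record the dates of questionnaire, disclosure and first session so that the order can be verified.

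The consent meeting in Section 22.0 already offers an in-person contact common to both arms, so the extra staff time is small. The real cost falls on patients who consent by phone: disclosure waits until they have completed the questionnaire at a visit, a short delay that may also carry over to their first session. Sample size, endpoints and intervention are unchanged. The change does not remove expectation effects in the week-12 score itself, which come with an open-label design.
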